#### **6.11.1.2. Clinical Laboratory Abnormalities**

All laboratory test values will be converted to international standardized units. If a lab value is reported using a non-numeric qualifier (e.g., less than ( $<$ ) a certain value, or greater than ( $>$ ) a certain value), the given numeric value will be used in the summary statistics, ignoring the non-numeric qualifier. Observed values and the change from baseline of clinical laboratory

assessments for hematology, chemistry, and urinalysis will be summarized by visit and cohort and treatment group. Shift table will be used to assess maximum increase and/or decrease in CTCAE grade during the study period in the following laboratory measurements:

- Hematology: Absolute lymphocyte count, absolute neutrophil count, hemoglobin, platelets, and white blood cell count.
- Clinical chemistry: creatinine, calcium, CO2, magnesium, potassium, and sodium.
- Liver Biochemistry Biomarkers: Alanine aminotransferase (ALT), Aspartate aminotransferase (AST), Gamma-glutamyl transferase ( $\gamma$ GT), Alkaline phosphatase, and Total bilirubin.

#### **6.11.1.3. Physical Examination Findings**

Physical examination findings will only be listed.

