	30. Any other condition which, in the opinion of the investigator would impede competence or compliance or possibly hinder completion of the study.
Sample Size	A sample size of 15 subjects per cohort is empirically determined to assess the safety of the dose and characterize the PK. The total number of subjects will be approximately 30; 20 treated with FT-4101 and 10 with placebo. With 10 evaluable subjects in the treated group and 10 evaluable subjects in the control group, there is 84% power to detect a difference of 20% between the high dose treated group (cohort B) and the pooled placebo subjects from cohorts A and B in MRI-PDFF, assuming a standard deviation of 14% using a one-sided Wilcoxon-Mann-Whitney test with an alpha of 0.05.
Statistical Methods	Data analyses will follow a statistical analysis plan (SAP). The overall safety profile of FT-4101 will be assessed as the percentage of participants experiencing TEAE, serious TEAEs, TEAEs leading to premature study drug discontinuation, and treatment-emergent clinically significant laboratory abnormalities. Safety analysis will involve examination of the descriptive statistics and individual subject listings for any effects of study treatment on clinical tolerability and safety. Efficacy, PK and PD assessments for all dose groups will be analysed using descriptive methods; figures (bar charts or line plots) may also be generated to visualize the data. The primary preliminary efficacy analysis of the reduction (absolute and relative) of % liver fat on magnetic resonance imaging-estimated proton density fat fraction (MRI-PDFF) at 12 weeks will be analyzed using a Wilcoxon rank-sum test. The test will be one-sided and use a significance level of 0.05. Subjects in each dose group will be tested against the pooled placebo subjects from each cohort. If more than one dose of FT-4101 is evaluated, control of the alpha level will be accomplished using Holm's Sequential Bonferroni procedure [Holm 1979] to test each FT-4101 dose against the pooled placebo subjects. The secondary preliminary efficacy analysis of the reduction (absolute and relative) of % liver fat on magnetic resonance imaging-estimated proton density fat fraction (MRI-PDFF) at 6 weeks will be analyzed similarly. The secondary preliminary efficacy analysis of the proportion of subjects with $\geq 30\%$ relative reduction in liver fat at week 12 assessed by MRI-PDFF will be analyzed using a Fisher's exact test.

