## 5.0 STUDY OBJECTIVES AND ENDPOINTS

### 5.1 Primary Objectives and Endpoints

To assess safety and tolerability of FT-4101 after administration of multiple doses in overweight/obese subjects with NASH by:

- Incidence of treatment-emergent adverse events (TEAEs)
- Incidence of clinical lab abnormalities
- Incidence and severity of clinical findings on physical examination
- Change from baseline in vital signs (blood pressure [BP], heart rate [HR], respiratory rate, and temperature])
- Change from baseline in 12-lead electrocardiogram (ECG) parameters

To assess the preliminary efficacy of FT-4101 on liver fat after administration of multiple doses in overweight/obese subjects with NASH by:

- Reduction (absolute and relative) of % liver fat on MRI-PDFF at 12 weeks

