#### **10.2 Recording of Adverse Events and Serious Adverse Events**

- Any AE that occurs after signing of ICF through 28 days after last dose of study drug(s) should be recorded on the AE eCRF.
- In order to avoid vague, ambiguous, or colloquial expressions, the AE should be recorded in standard medical terminology rather than the subject's own words.
- Whenever possible, the investigator should combine signs and symptoms that constitute a single disease entity or syndrome into a final diagnosis, if appropriate. For example, fever, cough, and shortness of breath may be reported as pneumonia, if that is the final diagnosis.
- Each AE is to be evaluated for duration, severity, seriousness, and causal relationship to the investigational drug. The action taken and the outcome must also be recorded.
- SAEs that occur during the study or within 28 days after last dose of study drug(s), whether related to study drug, must be immediately reported to the Sponsor/SAE designee. Clinical trial sites will enter SAE information directly into the EDC clinical database within 24 hours of knowledge of the event. After the 28-day reporting window, only SAEs assessed as related to study drug need to be reported.

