## 12.0 STATISTICAL METHODS

### 12.1 Statistical and Analytical Plans

██████████ will be responsible for the statistical services, including statistical analysis, statistical reports and the statistical analysis plan (SAP) to be developed prospectively prior to database final lock. With permission of the Sponsor, statistical services may be delegated under an agreement of transfer of responsibilities to a qualified vendor of ██████████.

The SAP will provide further details regarding the definition of analysis variables and analysis methodology to address all study objectives. It will also provide any changes or additions to the analyses that are not apparent in the protocol.

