## **12.6 Analysis and Endpoints**

### **12.6.1 Analysis of Primary Safety and Tolerability Endpoints**

To assess safety and tolerability of FT-4101 after administration of multiple doses in overweight/obese subjects with NASH by:

- Incidence of treatment-emergent adverse events (TEAEs)
- Incidence of clinical lab abnormalities
- Incidence and severity of clinical findings on physical examination

- Change from baseline in vital signs (blood pressure [BP], heart rate [HR], respiratory rate, and temperature])
- Change from baseline in 12-lead electrocardiogram (ECG) parameters

Safety and tolerability of the study drugs will be assessed by collection and review of adverse events, tolerability, laboratory parameters, physical examination, vital signs, and ECG parameters throughout the duration of the study. Safety analysis will involve examination of the descriptive statistics and individual subject listings for any effects of study treatment on clinical tolerability and safety.

AEs will be summarized using the safety set.

All AEs will be coded using MedDRA. Data will be summarized using preferred term and primary system organ class.

Adverse event summaries will include the overall incidence (by system organ class and preferred term), events by maximum intensity, event by relationship to study treatment, events leading to discontinuation of study drug, and serious adverse events. Physical exam, vital signs, ECG, and laboratory parameters (hematology, chemistry, and urinalysis) will be summarized descriptively by treatment group.

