## **6. STATISTICAL METHODS OF DATA ANALYSIS**

### **6.1. General Considerations**

Unless otherwise specified, all data will be provided in subject level listings in addition to summary tables or figures.

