## **7. CHANGES TO THE PLANNED ANALYSIS IN THE PROTOCOL**

Two-sample independent t-test will be carried out to compare liver fat (%) between FT-4101 treatment and the pooled placebo at 6 and 12 weeks as a supportive analysis, based on one-sided significance level of 0.05.

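### The SAP only lists physical examination findings, although they are a primary safety endpoint that the protocol says will be summarised by treatment group, and SAP Section 7 does not declare the change

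*SAP*

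**What the plan says.** Protocol 5.1 names "Incidence and severity of clinical findings on physical examination" as a primary safety endpoint. The same item stands in Protocol 2.0 and 12.6.1 and in SAP 2.1 and 6.11; SAP 6.11 introduces its list as the primary safety endpoints.

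The last sentence of Protocol 12.6.1 sets the analysis: "Physical exam, vital signs, ECG, and laboratory parameters (hematology, chemistry, and urinalysis) will be summarized descriptively by treatment group".

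SAP 6.11.1.3 consists of one sentence: "Physical examination findings will only be listed".

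The general rule in SAP 6.1 is: "Unless otherwise specified, all data will be provided in subject level listings in addition to summary tables or figures".

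On changes between the two documents, Protocol 12.1 says of the SAP: "It will also provide any changes or additions to the analyses that are not apparent in the protocol". SAP Section 7, the section for such changes, has one entry, which begins: "Two-sample independent t-test will be carried out to compare liver fat (%) between FT-4101 treatment and the pooled placebo".

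**The concern.** An endpoint defined as incidence and severity needs a count, a denominator and a severity distribution for each group. A listing shows individual records and gives none of these. The reader would have to choose a baseline, decide what counts as new or worse, and pick the denominator, and two readers could reach different figures.

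At stake is whether a named primary safety endpoint will be reported in the form the protocol promised. The omission looks out of place because SAP 6.12 plans descriptive summaries by group even for pregnancy tests and viral serology, and the only other data the SAP confines to a listing are eligibility data (SAP 6.5).

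**Working it through.** The documents give no figure to reproduce for this point, so the check is a comparison of texts.

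**1. Is it a primary endpoint in both documents?** Yes: Protocol 2.0, 5.1 and 12.6.1; SAP 2.1 and 6.11.

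**2. What is planned for each of the five primary safety endpoints?** Protocol 12.6.1 plans summaries for all five. The SAP plans:

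| Endpoint | SAP section | By-group summary in the SAP |
|---|---|---|
| TEAEs | 6.11.1.1 | Yes, by treatment group |
| Laboratory abnormalities | 6.11.1.2 | Yes, by visit, cohort and treatment group, with grade shifts |
| Physical examination findings | 6.11.1.3 | **No, listing only** |
| Vital signs | 6.11.1.4 | Yes, by visit, cohort and treatment group |
| 12-lead ECG | 6.11.1.5 | Yes, by visit, cohort and treatment group |

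Four of five have a summary; 5 − 4 = 1 does not.

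**3. Could the default in SAP 6.1 restore the summary?** No. That rule applies unless something else is specified, and the word *only* in 6.11.1.3 specifies otherwise.

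**4. Is the departure declared?** Not in Section 7. Its single entry concerns the supportive t-test on liver fat.

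**5. How much would the TEAE tables recover?** Most of what matters clinically. SAP 6.11.1.1 tabulates TEAEs by treatment group, with severity by CTCAE grade. Protocol 10.3.1 counts an asymptomatic clinical observation as Grade 1, so a new sign can qualify as an event. Protocol 7.3.3.1 ties the hair assessments directly to judging alopecia as an adverse event. Some findings would still not appear as themselves:
- Protocol 10.1.1 exempts three kinds of pre-existing item, provided they were recorded at screening.
- Protocol 10.1.2 exempts expected fluctuations of pre-existing conditions that fall short of a clinically significant worsening.
- Protocol 10.2 says that "the investigator should combine signs and symptoms that constitute a single disease entity or syndrome into a final diagnosis, if appropriate". A sign handled this way is still counted and graded, but under the diagnosis.

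**6. Do the documents let the TEAE tables serve as the examination endpoint?** No statement to that effect appears in either. TEAEs and examination findings are separate items in every endpoint list.

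**7. Can severity be tabulated?** Only in part. CTCAE grading in Protocol 10.3.1 is for adverse events, and Protocol 9.1.4 gives the Norwood and Savin scales for hair. Neither document gives a general severity scale for examination findings.

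**The case against.** The best case for leaving the text alone is that little is lost. Protocol 2.0 describes the overall safety profile through TEAEs, serious TEAEs, TEAEs leading to discontinuation and clinically significant laboratory abnormalities, and does not mention physical examination there. The skin, hair and eye rule for stopping dose escalation (Protocol 6.5.1) and Table 6-1 work on adverse events and their grades. With about 30 subjects, a reader can count from a listing. SAP 6.11.1.3 also states its rule openly, and Protocol 12.1 does not say in which section of the SAP a change must appear.

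Much of this stands, and it keeps the point minor. It does not remove the conflict: the last sentence of Protocol 12.6.1 names physical examination specifically, and the SAP tabulates the other four safety endpoints at the same group sizes.

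Three stronger readings should be resisted.
- A reader might infer that skin, hair or eye signals would go unreported by group. The documents do not support this, because such effects are expected to be captured as graded TEAEs.
- A reader might take the general sentence in the protocol, "Safety analysis will involve examination of the descriptive statistics and individual subject listings", to require both a summary and a listing for every parameter. It describes safety analysis as a whole; the promise for physical examination rests on the last sentence of 12.6.1 alone.
- A reader might infer concealment. The listing-only rule is in plain view; what is missing is its identification as a departure in Section 7.

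**Conclusion.** The inconsistency is real and certain on the text: one of five primary safety endpoints lacks the by-group summary that Protocol 12.6.1 promises, and SAP Section 7 does not say so. Its size is minor. No hypothesis test, alpha, power or sample size is affected, and most clinically relevant new or worsened findings should reach the TEAE tables. That last judgement assumes that investigators record such findings as adverse events as Protocol Section 10 directs. It is still worth correcting, because nothing in either document allows the TEAE tables to replace this endpoint and the repair is cheap.

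**What to change.** Replace the sentence in SAP 6.11.1.3 with a descriptive summary by treatment group on the Safety analysis set (SAP 4.2):
- number and percentage of subjects with any new or worsened post-baseline finding, by body system as recorded, relative to the baseline in SAP 6.1.3;
- worst post-baseline severity where a grade was recorded;
- the subject listing, kept as now.

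Nothing more elaborate is needed: Protocol 12.6.1 promises only a descriptive summary by group, so neither a prescribed list of body systems nor a shift table for the hair scales is required to meet it.

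If the sponsor prefers listing only, the alternative is to declare and justify that in SAP Section 7 and to align the endpoint wording in both documents and the last sentence of Protocol 12.6.1.

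The cost is one extra table from examinations already scheduled. It assumes that findings are captured by body system, which the documents do not show. Percentages will be coarse: with 10 planned subjects per FT-4101 dose and 5 + 5 = 10 on placebo if pooled, one subject moves a percentage by 1/10 = 10 points. Severity will be incomplete where no grade was recorded.

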#### **6.11.1.4. Vital Signs**

Observed values and the change from baseline in vital signs will be summarized by visit and cohort and treatment group.

#### **6.11.1.5. 12-Lead Electrocardiogram Assessments**

Observed values and the change from baseline in 12-lead ECG parameters will be summarized by visit and cohort and treatment group. In addition, a categorical analysis of QTcF interval will be performed for each time point. The number and percentage of subjects in each QTcF interval ( $\leq$ 450 msec,  $>$ 450 -  $\leq$ 480 msec,  $>$ 480 -  $\leq$ 500 msec, and  $>$ 500 msec) will be summarized.

Categories of changes in QTcF interval from baseline ( $\geq$ 30 msec and  $\geq$ 60 msec) will be tabulated as well.

QTcF will be summarized using a shift from baseline table to worst post-baseline change based on the categories described above. ECG interpretation will be summarized using a shift from baseline table to worst post-baseline assessment based on the categories of normal, abnormal not clinically significant, abnormal clinically significant, and not done/missing.

### **6.12. Other Laboratory Assessments**

Other laboratory assessments such as pregnancy tests (hCG and FSH) and serology (hepatitis B, hepatitis C, and HIV) will be summarized descriptively by visit and treatment group.

## **7. CHANGES TO THE PLANNED ANALYSIS IN THE PROTOCOL**

Two-sample independent t-test will be carried out to compare liver fat (%) between FT-4101 treatment and the pooled placebo at 6 and 12 weeks as a supportive analysis, based on one-sided significance level of 0.05.

## **8. STATISTICAL SOFTWARE**

All statistical analyses will be performed using SAS® version 9.4.

## 9. APPENDIX

### 9.1. APPENDIX A – Schedule of Events (SOE)

ASSESSMENT	SCREEN	RUN-IN PERIOD			IN-HOUSE PERIOD		OUTPATIENT VISITS										IN-HOUSE PERIOD		OUTPATIENT	FOLLOW-UP
		C1 D-45 to D-15	C1 D-14 (+1)	C1 D-11 (±1)	C1 D-7 (±1)	C1 b D-1	C1 b D1	C1 D15 (±1)	C2 c D1 (±1)	C2 D15 (±1)	C3 c D1 (±1)	C3 D15 (±1)	C4 c D1 (±1)	C4 D4 (±1)	C4 D8 (±1)	C4 b D14	C4 b D15	C4 d D22 (±1)	C4 e D29 (±2)	
Study Visit Cycle(C)/Day(D) (Visit Window) a																				
DOSING f						X		X		X		X		X	X	X	X			
Informed consent	X																			
Assess eligibility criteria	X	X																		
Demography	X																			
Medical history	X	X g																		
Weight	X	X	X	X		X	X	X	X	X	X	X	X	X	X	X	X	X	X	
BMI	X					X				X									X	
Height	X																			
Vital signs	X	X	X	X	X	X	X	X	X	X	X	X	X	X	X	X	X	X	X	
Physical examination (PE)	X																			X
Abbreviated PE						X		X	X	X	X	X	X	X					X	X
12-lead ECG	X						X		X		X		X							X
Hematology, serum chemistry & urinalysis	X						X	X	X	X	X	X	X	X					X	X
Coagulation	X						X				X									X
Fasting plasma glucose	X																			
Fasting lipid profile	X						X		X		X		X						X	X
TSH	X																			
HbA1c	X							X			X									X
Hep B, Hep C, HIV	X																			
Pregnancy test (serum)	X																			
Pregnancy test (urine)		X	X	X	X		X	X	X	X	X	X	X	X	X	X	X		X	
FSH for postmenopausal	X																			
Urine drug screen	X						X				X									X
Alcohol breath test	X	X	X	X	X	X	X	X	X	X	X	X	X	X	X	X	X	X	X	

ASSESSMENT	SCREEN	RUN-IN PERIOD			IN-HOUSE PERIOD		OUTPATIENT VISITS										IN-HOUSE PERIOD		OUTPATIENT	FOLLOW-UP
		C1 D-14 (+1)	C1 D-11 (±1)	C1 D-7 (±1)	C1 b D-1	C1 b D1	C1 D15 (±1)	C2 c D1 (±1)	C2 D15 (±1)	C3 c D15 (±1)	C3 D1 (±1)	C4 c D1 (±1)	C4 D4 (±1)	C4 D8 (±1)	C4 b D14	C4 b D15	C4 d D22 (±1)	C4 e D29 (±2)		
Study Visit Cycle(C)/Day(D) (Visit Window) a	C1 D-45 to D-15																			
Deuterated Water Labeling Period (3 x 50 mL/day) h		C1D-14 to C1/D-8													C4/D1 to C4/D7					
Blood collection for fasting hepatic DNL assessments i,j		X	X	X		X				X	X	X	X	X		X	X			
Blood collection for PK assessments k						X	X	X	X		X			X	X	X	X			
Sebum collection using Sebutape® for fatty acid concentration		X n				X								X			X	X		
Sebum collection using Sebutape® for DNL		X				X								X			X	X		
Sebumeter® for sebum production						X	X	X	X	X	X	X				X	X	X		
Blood collection for circulating biomarkers l						X				X							X	X		
FibroScan®(LSM and CAP)	X o																	X		
MRI-PDFF	X													X m				X m		
FibroSure®	X										X							X		
Randomization						X														
Record concomitant medications	X	X	X	X	X	X	X	X	X	X	X	X	X	X	X	X	X	X	X	
Record adverse events	X	X	X	X	X	X	X	X	X	X	X	X	X	X	X	X	X	X	X	
Deuterated water supply and accountability		X	X	X										X	X	X				
IP supply and IP accountability						X	X			X	X			X	X	X	X			
Subject Diary for -deuterated water intake -IP intake If T2DM glycemic control	X	X	X	X	X	X	X	X	X	X	X	X	X	X	X	X	X	X	X	
Standardized controlled conditions and meals						X	X									X	X			

aCycle (C) 1 Day (D) 1 (C1/D1) is the start of the four 21-day treatment cycles. Study visits occurring before C1/D1 are based on a countdown to this date. Subsequent study visits are defined by the days from the start of the most recent treatment cycle.

bStudy windows are not provided on these study dates. C1/D1 is the start of study treatment. C1/D-1 must occur on the day prior to C1/D1. C4/D14 and C4/D15 visits are required to occur starting on the last day of study treatment in cycle 4 (C4/D14), in order to obtain time and treatment day-dependent PK/PD samples.

cDay 1 of treatment cycles 2-4 expected to start 22 days (±1) from start of previous treatment cycle (except when dose delays required for AE's-see protocol).

dIn subjects who discontinue study participation before completion of the study treatment period in Cycle 4, the end of treatment (EOT) visit (C4/D22) should occur approximately ≥6 days from last dose of FT-4101/placebo.

eIn subjects who discontinue study participation before completion of the study treatment period in Cycle 4, a follow-up visit occurring approximately 28 days from the start of the last treatment cycle (Day1) is requested.

fDrug is administered QD on days 1-14 and held days 15-21 of each treatment cycle. Hold dose of IP in the morning of visits occurring during the active treatment period until all fasting visit procedures have been completed and as instructed per visit.

gInterim medical history

hEach bottle of deuterated water should be consumed at least 3 hours apart

iSubjects will be instructed to fast (no food or drink, except water) on the evening prior to the visit to ensure an approximate 10-hour fast prior to the fasted blood sample collection the next morning. Blood for DNL needs to be taken prior to consumption of deuterated water on C1/D-14, C1/D-11, C4/D1, and C4/D4. Blood samples for DNL are taken pre-dose on days IP is administered also.

jIncludes blood for deuterium enrichment in palmitate and body water. Samples should be collected same time of day.

kPK sampling will follow Appendix B (PK sampling schedule).

lSampling for fasting circulating biomarker include metabolic parameter (Lipids, FPG, fasting insulin, HOMA-IR, HbA1c, Adiponectin (total and high molecular weight), FGF-21, and Malonyl carnitine), liver injury and fibrosis biomarkers (CK-18 fragment, ELF score [HA, PIIINP, TIMP-1], PRO-C3).

mTo be performed within a window of 4 days prior to C3/D1 and C4/D22

nThese Sebutape samples collected at D-14 will be stored for potential future fatty acid analysis.

oThis FibroScan can be performed at screening or within 30 days prior to screening. Both LSM and CAP values are captured and recorded. Both LSM and CAP are PD endpoints but only CAP ( $\geq 300$ dB/m) is part of the eligibility criteria.

